11.6. Appendix 6: Derived and Transformed Data

11.6.1. General

Multiple Measurements at One Analysis Time Point

• If there are two values within a time window, the value closest to the target day for that window will be used. If values are the same distance from the target, then the mean will be taken.• Participants having both High and Low values for Normal Ranges at any post-baseline visit for safety parameters will be counted in both the High and Low categories of “Any visit post-baseline” row of related summary tables. This will also be applicable to relevant Potential Clinical Importance summary tables.
Study Day

• Calculated as the number of days from First Dose Date:
• Ref Date = Missing → Study Day = Missing• Ref Date < Treatment Start Date → Study Day = Ref Date – Treatment Start Date• Ref Date ≥ Treatment Start Date → Study Day = Ref Date – (Treatment Start Date) + 1

Example of Handling the Incorrect Treatment and Dose at the Timing of Onset of the AE								
--	--	--	--	--	--	--	--	--

Here are the examples 1- 3 which a given subject had the incorrect treatment in certain period or all periods in treatment period (week 0 to week 52). It is assumed that all participants here complete study (i.e., do not withdraw).

Example	1			2			3		
Dose group	FF/UMEC/VI 100/62.5/25			FF/UMEC/VI 100/62.5/25 to FF/UMEC/VI 200/62.5/25			FF/UMEC/VI 100/62.5/25		
allocated dose at week0	FF/UMEC/VI 100/62.5/25			FF/UMEC/VI 100/62.5/25			FF/UMEC/VI 200/62.5/25		
Switch treatment at week24	No			Yes			No		
Plan dose/ Actual dose/ dose at AE	Plan	Actual	dose at AE	Plan	Actual	dose at AE	Plan	Actual	dose at AE
week0 -4	FF100	FF100	FF100	FF100	FF100	FF100	FF200	FF100	FF100
week4 - 12	FF100	FF100	FF100	FF100	FF200	FF100	FF200	FF100	FF100
week12 - 24	FF100	FF100	FF100	FF100	FF100	FF100	FF200	FF100	FF100
week24 - 36	FF100	FF100	FF100	FF200	FF200	FF200	FF200	FF100	FF100
week36 - 52	FF100	FF200	FF100	FF200	FF100	FF200	FF200	FF100	FF100

Example 1 is the case that a given participant was allocated FF/UMEC/VI 100/62.5/25 at week0 and not switch the study treatment at week24, but had incorrect treatment (i.e., FF/UMEC/VI 200/62.5/25) at week 36 to 52. Therefore, as described in Section 5.1 and Section 8.2, dose group for this participant will be FF/UMEC/VI 100/62.5/25, and AE at week 36 – 52 will be handled as AE at FF/UMEC/VI 100/62.5/25 for dose at AE analyses.

Example 2 is the case that a given participant was allocated FF/UMEC/VI 100/62.5/25 at week0 and switched the study treatment at week24, but had incorrect treatment (i.e., FF/UMEC/VI 200/62.5/25 at week 4-12 and FF/UMEC/VI 100/62.5/25 at week 36-52) at two periods. Therefore, as described in Section 5.1 and Section 8.2, dose group for this participant will be FF/UMEC/VI 100/62.5/25 to FF/UMEC/VI 200/62.5/25, and AE at week 4 – 12 will be handled as AE at FF/UMEC/VI 100/62.5/25 and AE at week 36 – 52 will be handled as AE at FF/UMEC/VI 200/62.5/25 for dose at AE analyses.

Example 3 is the case that a given participant was allocated FF/UMEC/VI 200/62.5/25 at week0 and not switch the study treatment at week24, but had incorrect treatment (i.e., FF/UMEC/VI 100/62.5/25) during all periods. This participant HAD incorrect treatment during all periods. Therefore, as described in Section 5.1 and Section 8.2, dose group for this participant will be FF/UMEC/VI 100/62.5/25, and AE at any time will be handled as AE at FF/UMEC/VI 100/62.5/25 for dose at AE analyses.

11.6.2. Study Population

Demographics
Age

 Age will be calculated based on the Pre-Screening Visit date (or Screening, if pre-screening not performed). Birth date will be imputed as follows: 
 Any participant with a missing day and month will have this imputed as '30th June'. All participants with imputed age of 17 or 18 years will be source data verified, and presence / absence of protocol deviation on the inclusion criteria #1 will be taken into consideration in the derivation for the analysis variable age. Birth date will be presented in listings as 'YYYY'.
Age Category

 Age categories (unless otherwise specified) are based on age at Pre-screening and are defined as: 
 18 to < 65 65 to <75 years 75 to <85 years ≥ 85 years Age categories in age range summary for EudraCT are based on age at Pre-screening and are defined as: 
 Adolescents (12-17 years) Adult (18-64 years) ≥65-84 years ≥85 years
Body Mass Index (BMI)

 Calculated as Weight (kg) / Height (m)²
Cardiovascular History and Risk Factor

Cardiovascular history and risk factors will be assessed at Visit 1. Participants with one or more of the following terms recorded as either current or past medical conditions at Visit 1 is considered to have cardiovascular history/risk factors:
 
 Cardiovascular history 
 arrhythmia, congestive heart failure, coronary artery disease, myocardial infarction, cerebrovascular accidents, Cardiovascular risk factors 
 hypertension, diabetes mellitus hypercholesterolemia.

Treatment Compliance

- The actual total number of doses received by each participant will be calculated as the sum of (dose counter start value – dose counter stop value) over all inhalers dispensed to the participant during the treatment period, and percentage treatment compliance will be calculated as described in Section 6.1.5.

If a dose counter start count is missing then it will be assumed to be 30 for the Ellipta DPI. If a dose counter stop value is missing then number of doses received will be set to missing for that container.

Treatment compliance will be based only on the returned devices prior to or at end of study/early withdrawal visit that were dispensed during the treatment period.

- Overall compliance will be categorized as follows:
 - < 50 %
 - ≥50 % to < 80 %
 - ≥80 % to < 95 %
 - ≥95 % to ≤105 %
 - >105 % to ≤120 %
 - >120 %.
- If a participant receives a treatment other than the allocated treatment during the study, the compliance will still be calculated using data from all containers received and overall exposure start and stop dates
- In interim analysis, treatment compliance will be calculated based on data until the day before visit 5 (i.e., treatment stop date will be replaced with the day before visit 5).
- One dose per one day will be received in this study.

Derivation of Complete for Study Disposition in Interim Analysis

- In interim analysis, “completed” means completion of Visit 5 (Week 24 visit).
- If the response to the question “Did the subject fail to complete this phase of the study?” is “No” in eCRF, then this participant will be regarded as “completed” in interim analysis.

Derivation of % predicted FEV₁

- % predicted FEV₁ will be derived according to [Implementing GLI-2012 regression equations, July 16, 2015].

$$\% \text{ predicted FEV1} = (\text{measured FEV1 value} / M) \times 100$$

$$M = \exp(a_0 + a_1 \times \ln(\text{Height}) + a_2 \times \ln(\text{Age}) + a_6 + \text{Mspline})$$

Note: The integer value of calculated Age will be used in this study.

Note: ln() = natural log transformation.

Note: M is the predicted value of FEV₁.

Note: Since this study includes only Japanese participants, a₃ to a₅ are not used in this study. See Philip H. Quanjer et al (Philip, 2012) more detail.

- Coefficients of M

Derivation of % predicted FEV₁
--

Different coefficients of M need to be used for males and females.

	Coefficients of M in males	Coefficients of M in females
a ₀	-10.3420	-9.6987
a ₁	2.2196	2.1211
a ₂	0.0574	-0.0270
a ₆	-0.0708	-0.0708

- Mspline

Different Msplines need to be used depending on a participant's age and sex.

For 18-24 years, Msplines below will be used. These values come from "lookup tables" described in [Implementing [GLI-2012](#) regression equations, July 16, 2015].

Age	Mspline in males	Mspline in females
18	0.1924	0.1785
19	0.2029	0.1823
20	0.2081	0.1839
21	0.2091	0.1841
22	0.2071	0.1832
23	0.2030	0.1812
24	0.1970	0.1785

For 25-95 years, Mspline will be calculated by using the formula below and coefficients.

$$\text{Mspline} = b_0 + b_1 * (\text{Age}/100) + b_2 * (\text{Age}/100)^2 + b_3 * (\text{Age}/100)^3 + b_4 * (\text{Age}/100)^4 + b_5 * (\text{Age}/100)^5$$

	Coefficients of Mspline in males	Coefficients of Mspline in females
b ₀	0.3901	0.0552
b ₁	-1.0579	1.6029
b ₂	1.4743	-6.4845
b ₃	-2.1077	10.2723
b ₄	-0.1215	-9.8630
b ₅	0.8873	3.8802

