## 2. SCHEDULE OF ACTIVITIES (SOA)

Table 1 SCHEDULE OF ACTIVITIES

Procedure	Pre-screen	Run-in	Treatment period							Follow-up
Visit	0	1 Screening	2 Baseline	3	4	5	6	7 End of Treatment (EOT)	Early Withdrawal (EW)	Safety follow-up contact
Day	-28 to -14	-14	1	29	85	169	253	365		
Week	-4 to -2	-2	0	4	12	24	36	52		
Window		-3		-5/+2d	-5/+2d	-5/+2d	-5/+2d	-5/+2d		
Informed consent 	X									
Genetics/Pharmacogenetic informed consent 	X									
Inclusion and exclusion criteria		X	X							
Demography	X									
Past and current medical conditions including asthma history  and exacerbation history		X								
Smoking history and status		X								
Concomitant medication review		X	X	X	X	X	X	X	X	X
Allocation/registration 			X							
Register visit in IRT (RAMOS NG) 	X	X	X	X	X	X	X	X	X	X
Safety Assessment										
Physical examination		X				X		X	X	
Weight/height		X								
Adverse events			X	X	X	X	X	X	X	X
Serious adverse events	X	X	X	X	X	X	X	X	X	X
Vital signs (blood pressure and pulse rate)		X	X	X	X	X	X	X	X	
ECG		X		X		X		X	X	
Hematology and clinical chemistry		X			X	X		X	X	
Urinalysis		X			X	X		X	X	
Serum pregnancy test 		X			X	X		X	X	
Urine pregnancy test 			X	X			X			

Procedure	Pre-screen	Run-in	Treatment period							Follow-up
			2 Baseline	3	4	5	6	7 End of Treatment (EOT)	Early Withdrawal (EW)	
Visit	0	1 Screening								Safety follow-up contact
Day	-28 to -14	-14	1	29	85	169	253	365		
Week	-4 to -2	-2	0	4	12	24	36	52		
Window		-3		-5/+2d	-5/+2d	-5/+2d	-5/+2d	-5/+2d		
Other Assessment										
ACQ 		X 	X 			X 		X 	X 	
SGRQ 			X			X		X	X	
AQLQ 			X			X		X	X	
Pre-dose spirometry 			X			X		X	X	
Moderate/severe asthma exacerbation			X	X	X	X	X	X	X	X
Genetics/Pharmacogenetic sampling 			X							
Dispense paper Medical Problems/Medications Taken worksheet	X	X	X	X	X	X	X	X	X	
Review paper Medical Problems/Medications Taken worksheet		X	X	X	X	X	X	X	X	X
Healthcare resource utilization			X	X	X	X	X	X	X	
Dispense investigational product			X	X	X	X	X			
Collect investigational product				X	X	X	X	X		X
Dispense salbutamol (as required)		X	X	X	X	X	X			
Collect salbutamol (as required)			X	X	X	X	X	X	X	

1. The Informed Consent Form (ICF) must be signed before any study procedures, including medication cessation.

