**Figure 1 Study Schematic**

Eligible patients who meet the pre-defined criteria at screening (Visit 1) will enter into a 2-week run-in period. During the run-in period, the subjects will continue their pre-screening inhaled medications for asthma (ICS+ LABA or ICS+LABA+ LAMA) until the day before Visit 2 without any change in regimen/dosage. After completion of the run-in period, subjects who meet pre-defined criteria at Visit 2 will be allocated to either FF/UMEV/VI 100/62.5/25 mcg (Group 1) or FF/UMEV/VI 200/62.5/25 mcg (Group 2) depending on the asthma control status with inhaled asthma therapy during the run-in period (see [Table 2](#)), and initiate a 52-week treatment period. Only at Week 24 of the treatment period (Visit 5), switching medication from FF/UMEV/VI 100/62.5/25 mcg to FF/UMEV/VI 200/62.5/25 mcg will be permitted if the control status of the subject assessed by ACQ-7 is inadequate (i.e., ACQ score >0.75). As a rescue medication, salbutamol is permitted throughout the run-in and treatment periods.

**Table 2 Correspondence between Asthma Control Status with Inhaled Asthma Therapy during the run-in period and Allocated Study Treatment**

Group	Asthma control status with inhaled asthma therapy 	Allocated study treatment
Group 1	Not well controlled with ICS (mid-dose)+LABA or Controlled with ICS (mid-dose)+LABA + LAMA	FF/UMEV/VI 100/62.5/25 mcg via ELLIPTA, once-daily, 1 puff/time, morning
Group 2	Not well controlled with ICS (high-dose)+LABA or Not well controlled with ICS (mid-dose)+LABA + LAMA or Controlled with ICS (high-dose)+LABA + LAMA	FF/UMEV/VI 200/62.5/25 mcg via ELLIPTA, once-daily, 1 puff/time, morning

1. Asthma Control Questionnaire (ACQ-6 at screening and ACQ-7 at week 0, week 24, week52/Withdrawal) will be used for the assessment of control status of asthma, i.e.,  $\leq 0.75$  points shows controlled and  $>0.75$  shows not well controlled.

Subjects will visit the clinic/hospital at screening (Visit 1), Week 0 (Visit 2), Week 4 (Visit 3), Week 12 (Visit 4), Week 24 (Visit 5), Week 36 (Visit 6), Week 52 (Visit 7/End of Treatment [EOT]) or Early Withdrawal (EW) , and about one week after Week 52 (Visit 7/EOT) or EW Visit as a safety follow-up visit.. Telephone contact can be selected for follow-up period.

This study consists of three periods as described below: run-in, treatment and follow-up periods. Details of study procedures and assessments in these periods are provided in the Study Reference Manual (SRM).

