6.1.5. Treatment Compliance

Treatment compliance will be assessed during the treatment period by dose group and total.

For the treatment period, the actual total number of doses received by each subject will be calculated as the sum of (dose counter start value – dose counter stop value) over all inhalers dispensed to the subject during the treatment period and returned prior to or at the EOT/EW visit, and percentage compliance will be calculated as follows:

$$\text{Treatment Compliance} = \frac{\text{total number of doses received}}{\text{treatment stop date} - \text{treatment start date} + 1} \times 100.$$

In interim analysis, treatment compliance will be calculated based on data until the day before visit 5 (i.e., treatment stop date will be replaced with the day before visit 5). Details on the derivations are provided in Section 11.6.2.

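### Compliance counts doses only from inhalers returned by EOT/EW but divides by all treatment days, so an unreturned used inhaler lowers reported compliance

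*SAP*

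**What the plan says.** **Numerator.** SAP 6.1.5 adds up counter start minus counter stop "over all inhalers dispensed to the subject during the treatment period and returned prior to or at the EOT/EW visit". In SAP 11.6.2 the first bullet sums "over all inhalers dispensed to the participant during the treatment period" and then refers back to 6.1.5 for the percentage. A later sentence there restates the limit: "Treatment compliance will be based only on the returned devices prior to or at end of study/early withdrawal visit".

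**Denominator.** SAP 6.1.5 uses all days from treatment start to treatment stop, both included. At the interim, "treatment stop date will be replaced with the day before visit 5". Neither section adjusts the day count for a device that did not come back.

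**Missing counts.** SAP 11.6.2 assumes 30 when a start count is missing. For the stop count: "If a dose counter stop value is missing then number of doses received will be set to missing for that container". It does not say whether the participant's total then skips that container or itself becomes missing.

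**Reporting.** "Overall compliance will be categorized as follows": below 50%, 50 to below 80%, 80 to below 95%, 95 to 105%, above 105 to 120%, and above 120%. The results appear in Tables 1.24 and 11.22 and Listings 14 and 57.

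**The concern.** Numerator and denominator cover different things. A lost, forgotten or late inhaler removes its doses from the numerator, while the days on which it was used stay in the denominator. The formula then reports non-adherence where there is only an incomplete device record. The direction is fixed, because leaving out a non-negative count can only lower the ratio.

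The SAP handles missing components with more care elsewhere. For the ACQ and AQLQ scores in SAP 11.6.4, an allowed missing item is taken out of the denominator, and the score becomes missing when too much is absent. Compliance has no such rule.

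The stake is modest but real. Exposure in SAP 8.1 is summarised by duration, so the compliance table is the planned summary of doses actually taken in a long-term safety study. The interim version belongs to the Week 24 package that Protocol 10.3.4 intends for the Japanese submission.

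**Working it through.** **Inputs**
- One dose a day: SAP 11.6.2.
- 30 doses per inhaler: Protocol 7.1, Table 4.
- Visit 5 on Day 169 and Visit 7 on Day 365, each with a window of -5/+2 days: Protocol Table 1.
- Last dose taken at Visit 7: Protocol 7.2. On nominal days the Week 52 denominator is therefore 365.
- Interim period ends the day before Visit 5: SAP 6.1.5. On nominal days the interim denominator is 168.
- Rate of unreturned devices: not given. One unreturned inhaler is an illustration, not an estimate.

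**Formula (SAP 6.1.5).** Compliance = 100 x (doses from counted inhalers) / (days on treatment).

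**Starting check.** The documents state no compliance figure to reproduce. With every device returned, a fully adherent participant has 365/365 = 100% at Week 52 and 168/168 = 100% at the interim, as intended.

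**One full inhaler unreturned, fully adherent participant, nominal days**
- Week 52: (365 - 30)/365 = 335/365 = 91.8%.
- Interim: (168 - 30)/168 = 138/168 = 82.1%.

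Both fall in the 80 to below 95% category instead of 95 to 105%.

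**Doses that must go uncounted to drop below 95%**
- Week 52: 5% of 365 = 18.25. Losing 18 gives 347/365 = 95.1%; losing 19 gives 346/365 = 94.8%.
- Interim: 5% of 168 = 8.4. Losing 8 gives 160/168 = 95.2%; losing 9 gives 159/168 = 94.6%.

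**Does one lost inhaler always change the category?** No. These cases stay within the visit windows and assume each inhaler is finished before the next is opened, which the documents do not state.
- Final: Visit 6 on Day 255 and Visit 7 on Day 360. The last interval has 360 - 255 + 1 = 106 doses, or 30 + 30 + 30 + 16. Losing the 16-dose inhaler gives (360 - 16)/360 = 344/360 = 95.6%.
- Interim: Visit 3 on Day 24, Visit 4 on Day 87, Visit 5 on Day 169. The intervals hold 23, 63 (30 + 30 + 3) and 82 (30 + 30 + 22) doses, total 168. Losing the 3-dose inhaler gives 165/168 = 98.2%. Losing both the 3-dose and 22-dose inhalers gives 143/168 = 85.1%.

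**Container with no stop count.** If it is skipped, the result is the same as for an unreturned device. If the participant's total becomes missing, there is no downward error but the participant has no value. The SAP text allows either.

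**The case against.** **Safeguards.** Protocol 7.1 requires all used and unused product to be returned, and Protocol 7.6 requires dispensed and taken product to be recorded and reconciled. The final cut-off is EOT/EW rather than each visit, so an inhaler forgotten at an intermediate visit can still come back and count. This stands: few participants may be affected. It limits how often the formula fails, not how it behaves when a device is missing.

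**Consequence.** Compliance is descriptive, the study has no hypotheses (SAP 2.4), and no per-protocol population is defined (SAP 11.1). This also stands. No endpoint, exposure summary or event rate uses the compliance figure.

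Three stronger readings are tempting but not supported.

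- *Any single unreturned inhaler moves a participant out of the 95-105% category, and two at the interim always give less than 80%.* The 95.6%, 98.2% and 85.1% cases above contradict this within the permitted windows.
- *SAP 11.6.2 contradicts itself.* Its first bullet has no return condition but defers to 6.1.5, which has one, and the later sentence repeats it. This is loose wording; the rule is returned devices only.
- *Early withdrawers systematically lose their last dispensing interval.* Both schedules (Protocol Table 1, SAP 11.2.1) leave "Collect investigational product" blank at EW and mark it at the follow-up contact, after the SAP's cut-off. But Protocol 7.2 allows the last dose to be taken at the EW visit, and Protocol 7.6 has doses counted at clinic visits, so the device may well be present at EW. Protocol 5.1 adds "Telephone contact can be selected for follow-up period". These passages need reconciling, but no size can be attached to them.

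**Conclusion.** The point holds as a minor defect in a descriptive derivation. Under the returned-only rule, doses taken from an unreturned used inhaler count as not taken over days that still count. The same follows for an inhaler with no stop value if that container is skipped. The error can only be downward.

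The sizes of 91.8% at Week 52 and 82.1% at the interim rest on full adherence, nominal visit days and a full 30-dose inhaler. Part-used inhalers give smaller effects, sometimes with no change of category. How many participants would be affected cannot be derived from the documents. The reach is Tables 1.24 and 11.22 and Listings 14 and 57.

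**What to change.** State one rule, in the same words, in SAP 6.1.5 and 11.6.2.

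1. Count every study inhaler with a recorded stop value, including one returned after EOT/EW up to the follow-up contact. At the interim, count inhalers dispensed before Visit 5 whose stop value is recorded by the interim data lock.
2. If an inhaler that may have been used is unreturned or has no stop value, do not score its doses as zero in the category table. Show the participant in a separate row for incomplete device return, with the number of such participants, and give the documented-dose percentage in the listing as a lower bound.

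Shortening the denominator instead would restore 335/335 = 100% and 138/138 = 100% in the illustration, but it needs an assumption about which days the missing device covered. The separate row avoids that.

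Separately, reconcile the blank EW cell for product collection with the SAP's EW cut-off and with Protocol 7.2 and 7.6.

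**Cost.** Items 1 and 2 are SAP wording and use data largely collected already, with no extra visits. A telephone follow-up may yield no device to read, and that participant then goes in the separate row. The EW cell sits in a protocol table, so it needs an amendment or a documented clarification. The downside is that some participants, possibly including poor adherers who do not return devices, leave the numeric categories; the separate row keeps them visible.

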11.6.3. Safety

Adverse Events
Adverse Event Rate
Event rate per thousand person-years will be displayed for AE data in separate tables as listed in Section 11.11.5 and Section 11.11.6. Event rate per thousand person-years will be calculated as the number of events x 1000 divided by the total participant exposure during the time-period of interest (i.e., during treatment period).
AE'S OF Special Interest
Adverse events of special interest have been defined as AEs which have specified areas of interest. These consist in groupings of preferred terms based on the MedDRA dictionary version used in each reporting effort. Subgroups may be defined, based on relevant combination of preferred terms, or on Standardized MedDRA queries (SMQ).

11.6.4. Other

Asthma Control Questionnaire (ACQ), ACQ-6 and ACQ-7												
General												

 All 6 or 7 items (5 most important symptoms, one question about CCI [REDACTED] and one about CCI [REDACTED] of ACQ have response on 0-6 ordinal scale (CCI [REDACTED] [REDACTED]). The total score is calculated as the average of all non-missing item responses [Asthma Control Questionnaire, Background, Administration and Analysis, April, 2008]. ACQ-6 will be used at screening (visit 1). ACQ-7 will be used at all visit 2, 5, 7 or EW visit. 												
Questions, Responses and Calculation Method for ACQ												

 Table below shows questions of ACQ. Each question has the response on 0-6 ordinal scale (CCI [REDACTED] [REDACTED]). The wordings of responses are not the same for all responses, but they are not described in this RAP. The total score for ACQ-7 is the mean of the response to the 7 questions. The total score for ACQ-6 is the mean of the response to the 6 questions excluding a question about CCI [REDACTED] [REDACTED] 												

  
 Question	Item	
   
 	CCI - This section contained Clinical Outcome Assessment data collection questionnaires or indices, which are protected by third party copyright laws and therefore have been excluded.	
 
 		
 
 		
 
 		
 
 		
  
	Question	Item		CCI - This section contained Clinical Outcome Assessment data collection questionnaires or indices, which are protected by third party copyright laws and therefore have been excluded.								
Question	Item											
	CCI - This section contained Clinical Outcome Assessment data collection questionnaires or indices, which are protected by third party copyright laws and therefore have been excluded.											

Asthma Control Questionnaire (ACQ), ACQ-6 and ACQ-7

	
CCI - This section contained Clinical Outcome Assessment data collection questionnaires or indices, which are protected by third party copyright laws and therefore have been excluded.
	

Handling of Missing Items

- Only one of the first five item responses are allowed to be missing in calculating the total scores for all versions of ACQ. One question about CCI (item 6) and one about CCI (item 7, for ACQ-7 only) are not allowed to be missing.
- If one of the first five item responses is missing, then total score will be calculated based on just the available data. This means missing value will be excluded from the denominator.

If there are unacceptable missing items, then ACQ will be regarded as missing.

Example

		Visit 2	Visit 5	Visit 7
Item 1	4	6	3	
Item 2	3	5	4	
Item 3	4	4	3	
Item 4	5	5	4	
Item 5	2	Missing	3	
Item 6	4	4	2	
Item 7	1	3	Missing	

- ACQ-7 score at visit 2: $(4 + 3 + 4 + 5 + 2 + 4 + 1) / 7 = 3.3$

Since there is no missing value, ACQ-7 is calculated by using all 7 responses. Data will be rounded to one decimal place.

- ACQ-7 score at visit 5: $(6 + 5 + 4 + 5 + 4 + 3) / 6 = 4.5$

Since there is one missing value for the first five item, ACQ-7 is calculated by using 6 responses.

- ACQ-7 score at visit 7: missing

Since question about CCI is missing, ACQ-7 should not be calculated and be missing at this visit.

St. George's Respiratory Questionnaire (SGRQ)

General

- Details for how to score the SGRQ, including handling of missing data, are outlined in the SGRQ manual (June, 2009).
- Changes from baseline in total score will be calculated.

Questions, Response and Weight for SGRQ

- Table below shows questions and responses of SGRQ, their weight for SGRQ score calculation and its number in aCRF.
- Each questionnaire response has a unique 'weight' to be used for score calculation.
- This questionnaire requests a single response to questions **CCI**, **CCI** and **CI**. If multiple responses are given to one of these questions, then averaging the weights for the positive responses for that question are acceptable.
- SGRQ has three components: **Symptoms; Activity; Impacts**

SYMPTOMS COMPONENT

- This is calculated from the summed weights for the positive responses to questions **CCI**.

ACTIVITY COMPONENT

- This is calculated from the summed weights for the positive responses to questions **CI** and **CI**.

IMPACTS COMPONENT

- This is calculated from the summed weights for the positive responses to questions **CCI**, **CCI** and **CCI**.

TOTAL SCORE

[figure not shown]
- The Total score is calculated by summing all positive responses in the questionnaire and expressing the result as a percentage of the total weight for the questionnaire

Calculation method is described in next box.

Question	Item	Number in aCRF	Response	Weight
CCI - This section contained Clinical Outcome Assessment data collection questionnaires or indices, which are protected by third party copyright laws and therefore have been excluded.				

St. George's Respiratory Questionnaire (SGRQ)

CCI - This section contained Clinical Outcome Assessment data collection questionnaires or indices, which are protected by third party copyright laws and therefore have been excluded.

[figure not shown]
St. George's Respiratory Questionnaire (SGRQ)

CCI - This section contained Clinical Outcome Assessment data collection questionnaires or indices, which are protected by third party copyright laws and therefore have been excluded.

St. George's Respiratory Questionnaire (SGRQ)

CCI - This section contained Clinical Outcome Assessment data collection questionnaires or indices, which are protected by third party copyright laws and therefore have been excluded.

St. George's Respiratory Questionnaire (SGRQ)

CCI - This section contained Clinical Outcome Assessment data collection questionnaires or indices, which are protected by third party copyright laws and therefore have been excluded.

Calculation Method

Each component of the questionnaire is scored separately in three steps:

- I. The weights for all items with positive responses are summed.
- II. The weights for missed items are deducted from the maximum possible weight for each component. The weights for all missed items are deducted from the maximum possible weight for the Total score.
- III. The score is calculated by dividing the summed weights by the adjusted maximum possible weight for that component and expressing the result as a percentage:

Score = CCI - This section contained Clinical Outcome Assessment data collection questionnaires or indices, which are protected by third party copyright laws and therefore have been excluded.

The Total score is calculated in similar way:

Score = CCI - This section contained Clinical Outcome Assessment data collection questionnaires or indices, which are protected by third party copyright laws and therefore have been excluded.

Sum of maximum possible weights for each component and Total:

- Symptoms: CCI
- Activity: CCI
- Impacts: CCI
- Total: CCI

Handling of Missing Items**Symptoms**

The Symptoms component will tolerate **a maximum of 2 missed items**. The weight for the missed item is subtracted from the total possible weight for the Symptoms component (CCI) and from the Total weight (CCI).

Activity

The Activity component will tolerate **a maximum of 4 missed items**. The weight for the missed item is subtracted from the total possible weight for the Activity component (CCI) and from the Total weight (CCI).

St. George's Respiratory Questionnaire (SGRQ)

Impacts

The Impacts component will tolerate **a maximum of 6 missed items**. The weight for the missed item is subtracted from the total possible weight for the Impacts component ($CC1$) and from the Total weight ($CC1$).

If there were unacceptable number of missed items for any component, then SGRQ total score will be handled as missing.

Example

Table below is example data for calculation of SGRQ total score. Since this questionnaire requests a single response to questions $CC1$, $CC1$ and C , this table shows only one selected response for questions $CC1$, $CC1$ and $CC1$ (Data columns are $CC1$). For other questions, this table shows the results of $CC1$ or $CC1$. In this example, it is assumed that there is no missed item.

In this study, each component score will not be calculated. However, we would like to show how to calculate each component score and total score in this example.

Symptoms

This is calculated from the summed weights for the positive responses to questions $CC1$. In this example, weights for $CC1$ data for questions $CC1$ need to be summed. Summed weight is $(CC1) = CC1$. Since maximum possible weight for symptoms is $CC1$, symptoms component score can be calculated as $CC1$.

Activity

This is calculated from the summed weights for the positive responses to questions C and C . In this example, weights for $CC1$ data for questions $CC1$ and $CC1$ need to be summed. Summed weight is $(CC1) = CC1$. Since maximum possible weight for activity is $CC1$, symptoms component score can be calculated as $CC1$.

Impacts

This is calculated from the summed weights for the positive responses to questions $CC1$, $CC1$ and $CC1$. In this example, weights for $CC1$ data for questions $CC1$, $CC1$ and weights for $CC1$ data for questions $CC1$, $CC1$ need to be summed. Summed weight is $(CC1) = CC1$. Since maximum possible weight for impacts is $CC1$, symptoms component score can be calculated as $CC1$.

Total

The Total score is calculated by summing all positive responses in the questionnaire and expressing the result as a percentage of the total weight for the questionnaire. Summed weights for total is summed weights for three components above, $(CC1) = CC1$. Since maximum possible weight for total score is $CC1$, SGRQ total score can be calculated as $CC1$.

[figure not shown]
St. George's Respiratory Questionnaire (SGRQ)

Question	Item	Response	Weight	Data
----------	------	----------	--------	------

CCI - This section contained Clinical Outcome Assessment data collection questionnaires or indices, which are protected by third party copyright laws and therefore have been excluded.

[figure not shown]
St. George's Respiratory Questionnaire (SGRQ)

CCI - This section contained Clinical Outcome Assessment data collection questionnaires or indices, which are protected by third party copyright laws and therefore have been excluded

[figure not shown]

St. George's Respiratory Questionnaire (SGRQ)

CCI - This section contained Clinical Outcome Assessment data collection questionnaires or indices, which are protected by third party copyright laws and therefore have been excluded

CCI - This section contained Clinical Outcome Assessment data collection questionnaires or indices, which are protected by third party copyright laws and therefore have been excluded

Asthma Quality of Life Questionnaire (AQLQ)**General**

- Details for how to score the AQLQ, including handling of missing data, are outlined in the [AQLQ](#) manual (June, 2005).
- Changes from baseline in total score will be calculated for the converted scores.

Questions, Responses and Calculation Method for AQLQ

- Table below shows questions of AQLQ.
- Each question has the response on a 7 – point scale ([CCI](#) [REDACTED], [CCI](#) [REDACTED] [CCI](#) [REDACTED]). The wordings of responses are not the same for all responses, but they are not described in this RAP.
- Individual items are equally weighted. The overall AQLQ score is the mean of the responses to each of the 32 questions. Therefore, AQLQ score can be calculated to add all 32 responses together and divided the total by 32.
- AQLQ has four domains: Activity limitations, Symptoms, Emotional function, Environmental stimuli
 - Activity limitations: item: [CCI](#) [REDACTED]
 - Symptoms: item: [CCI](#) [REDACTED]
 - Emotional function: item: [CCI](#) [REDACTED]
 - Environmental stimuli: item: [CCI](#) [REDACTED]
- Note that only AQLQ total score will be calculated in this study, not each domain score. But acceptable missing items depends on each domain. Handling of missing items is described in next section

Question	Item
CCI - This section contained Clinical Outcome Assessment data collection questionnaires or indices, which are protected by third party copyright laws and therefore have been excluded	

CCI - This section contained Clinical Outcome Assessment data collection questionnaires or indices, which are protected by third party copyright laws and therefore have been excluded

Handling of Missing Items

- Acceptable number of missed items
 - Activity limitations and Symptoms: **only one missing value per domain**
 - Emotional function, Environmental stimuli: **Not accept any missing responses**
- If there are missing items, then total score will be calculated based on just the available data.

This means missing value will be excluded from the denominator.

- If there were unacceptable number of missed items for any component, then AQLQ total score will be handled as missing.

Example

	Visit 2	Visit 5	Visit 7	
Item 1	3	missing	5	
Item 2	4	1	6	
Item 3	3	2	5	
Item 4	4	2	3	
Item 5	2	2	4	
Item 6	1	missing	5	
Item 7	4	1	missing	
Item 8	6	4	7	
Item 9	4	2	6	
Item 10	3	3	5	
Item 11	4	5	4	
Item 12	5	2	3	
Item 13	4	4	2	
Item 14	2	2	1	
Item 15	3	3	2	
Item 16	4	4	3	
Item 17	5	5	4	
Item 18	6	2	5	
Item 19	2	3	6	
Item 20	4	4	7	
Item 21	5	5	4	
Item 22	6	7	4	
Item 23	3	4	4	
Item 24	2	2	5	
Item 25	4	4	6	
Item 26	5	5	7	
Item 27	6	6	3	
Item 28	2	6	4	
Item 29	4	2	5	
Item 30	5	5	6	
Item 31	6	5	2	
Item 32	4	5	3	

- AQLQ total score at visit 2: $(3 + 4 + 3 + , , , + 5 + 6 + 4) / 32 = 3.9$

Since there is no missing value, AQLQ total score is calculated by using all 32 responses. Data will

be rounded to one decimal place.

- AQLQ total score at visit 5: $(1 + 2 + 2 + , , , + 5 + 5 + 5) / 30 = 3.6$

Although there is one missing value for Activity limitations domain (item 1) and one for Symptoms domain (item 6), the number of missed items is acceptable. AQLQ total score is calculated by using 30 responses available.

- AQLQ total score at visit 7: missing

Since one response for Emotional function domain (item 7) is missing and this is not acceptable, AQLQ total score should not be calculated and be missing at this visit.

